APPENDIX G. ESTIMANDS AND INTERCURRENT EVENTS

Label	Description
IcEv1 (Co-infection)	Co-infection with respiratory pathogens other than SARS-CoV-2 from administration of drug through Day 29
IcEv2 (Prohibited COVID-19 vaccine)	COVID-19 vaccine through Day 29 from administration of drug
IcEv3 (Prohibited treatments for COVID-19)	Use of prohibited treatments for COVID-19 from administration of drug through Day 29

APPENDIX H. PRIMARY AND KEY SECONDARY OBJECTIVES AND ESTIMANDS

Objective	Primary: To evaluate the efficacy of ADG20 compared to placebo in the treatment of mild or moderate COVID-19 in participants at high risk of disease progression	Primary: To evaluate the efficacy of ADG20 compared to placebo in the treatment of mild or moderate COVID-19 in participants at high risk of disease progression	Key Secondary: To evaluate the effect of ADG20 on the following clinical parameters in participants with mild or moderate COVID-19 and high risk of disease progression	Key Secondary: To evaluate the effect of ADG20 on the following clinical parameters in participants with mild or moderate COVID-19 and high risk of disease progression
Estimand Label	Estimand 1a (Primary)	Estimand 1b (Supplementary to Primary)	Estimand 2 (Key Secondary 1)	Estimand 3 (Key Secondary 2)
Estimand Description (with Endpoint)	Treatment difference (ADG20 – Placebo) in proportion of COVID-19-related hospitalization or all-cause death through Day 29 regardless of co-infection with respiratory pathogens other than SARS-CoV-2, use of prohibited COVID-19 vaccine, or prohibited treatments for COVID-19	Treatment difference (ADG20 – Placebo) in proportion of COVID-19-related hospitalization or all-cause death through Day 29 regardless of co-infection with respiratory pathogens other than SARS-CoV-2 or use of COVID-19 vaccine and assuming no intake of prohibited treatments for COVID-19	Treatment difference (ADG20 – Placebo) in proportion of participants experiencing severe/critical COVID-19 or all-cause death through Day 29 regardless of co-infection with respiratory pathogens other than SARS-CoV-2, use of prohibited COVID-19 vaccine, or prohibited treatments for COVID-19	Treatment difference (ADG20 – Placebo) in proportion of participants experiencing COVID-19-related emergency room visits, hospitalization, or all-cause death through Day 29 regardless of co-infection with respiratory pathogens other than SARS-CoV-2, use of prohibited COVID-19 vaccine, or prohibited treatments for COVID-19
Target Population	Adult and adolescent participants with laboratory confirmed mild or moderate COVID-19 who are at high risk of disease progression	Same as Estimand 1a	Same as Estimand 1a	Same as Estimand 1a
Endpoint	Incidence of COVID-19-related hospitalization or all-cause death through Day 29	Same as Estimand 1a	Incidence of severe/critical COVID-19 or all-cause death through Day 29	Incidence of COVID-19-related emergency room visits, hospitalizations, or all-cause death through Day 29
Treatment Conditions	IM ADG20, IM Placebo	Same as Estimand 1a	Same as Estimand 1a	Same as Estimand 1a
Population-Level Summary	Difference in proportion of COVID-19-related hospitalization or all-cause death through Day 29	Difference in proportion of COVID-19-related hospitalization or all-cause death through Day 29	Difference in proportion of severe/critical COVID-19 or all-cause death through Day 29	Difference in proportion of COVID-19-related emergency room visits, hospitalization, or all-cause death through Day 29

Objective	Primary: To evaluate the efficacy of ADG20 compared to placebo in the treatment of mild or moderate COVID-19 in participants at high risk of disease progression	Primary: To evaluate the efficacy of ADG20 compared to placebo in the treatment of mild or moderate COVID-19 in participants at high risk of disease progression	Key Secondary: To evaluate the effect of ADG20 on the following clinical parameters in participants with mild or moderate COVID-19 and high risk of disease progression	Key Secondary: To evaluate the effect of ADG20 on the following clinical parameters in participants with mild or moderate COVID-19 and high risk of disease progression
Estimand Label	Estimand 1a (Primary)	Estimand 1b (Supplementary to Primary)	Estimand 2 (Key Secondary 1)	Estimand 3 (Key Secondary 2)
IcEv1 (Co-Infection)	Treatment policy	Treatment policy	Treatment policy	Treatment policy
IcEv2 (Prohibited COVID-19 vaccine)	Treatment policy	Treatment policy	Treatment policy	Treatment policy
IcEv3 (Prohibited treatments for COVID-19)	Treatment policy	Hypothetical	Treatment policy	Treatment policy
Rationale for Strategies	Given the trial's confirmatory setting, interest lies in estimating treatment effects in participants who have access to prohibited concomitant therapy such as COVID-19 vaccines or treatments and regardless of co-infection with respiratory pathogens other than SARS-CoV-2, since this scenario reflects general clinical practice and the continuously evolving setting for preventing and treating COVID-19.	Interest lies in estimating the effectiveness of ADG20 against hospitalization or all-cause death without the influences of prohibited treatments for COVID-19.	Similar to Estimand 1a	Similar to Estimand 1a

APPENDIX I. OVERVIEW OF STATISTICAL METHODS: ESTIMATIONS OF ESTIMANDS AND SENSITIVITY ANALYSES

Estimand Label	Estimand Description	Main Estimation			Sensitivity Analysis
		Analysis Set	Imputation/Data Handling Rules	Analysis Model/Method	
Estimand 1a	Treatment difference (ADG20 – Placebo) in proportion of COVID-19-related hospitalization or all-cause death through Day 29 regardless of intake of prohibited treatments for COVID-19	FAS	The endpoint will incorporate all available information through Day 29. Where participants have missing primary endpoint through Day 29, the status will be imputed as not having COVID-19-related hospitalization or all-cause death (ie, responder)	The endpoint will be analyzed using the methodology for determining a standardized estimator for a binary outcome, with adjustment for prognostic factors. The standard error of the standardized estimator will be estimated using the delta method (refer to Appendix K)	Multiple imputation under MAR assumption followed by calculation of standardized risk difference and 95% CI using Rubin's method. Control based imputation Per-protocol Set analysis
Estimand 1b	Treatment difference (ADG20 – Placebo) in proportion of COVID-19-related hospitalization or all-cause death through Day 29 assuming no intake of prohibited treatments for COVID-19	FAS	In case of prohibited treatments for COVID-19, the primary endpoint will utilize multiple imputation under MAR assumption. The imputation model will be informed by the observed outcomes from participants who did not receive such medication (or received it after meeting the primary endpoint). The logistic model will include the prognostic factors.	Same as Estimand 1a	Hypothetical strategy of handling the ICEs.
Estimand 2	Treatment difference (ADG20 – Placebo) in proportion of participants experiencing severe/critical COVID-19 or all-cause death through Day 29 in the target population	FAS	Same as Estimand 1a	Treatment difference in the proportion of participants with severe/critical COVID-19 or all-cause death through Day 29 will be presented and tested using the main analysis method outlined for Estimand 1a	

Estimand Label	Estimand Description	Main Estimation			Sensitivity Analysis
		Analysis Set	Imputation/Data Handling Rules	Analysis Model/Method	
Estimand 3	Treatment difference (ADG20 – Placebo) in proportion of participants experiencing COVID-19-related emergency room visits, COVID-19-related hospitalization, or all-cause death through Day 29 in the target population	FAS	Same as Estimand 1a	Treatment difference in proportion of participants with COVID-19-related emergency room visits, COVID-19-related hospitalizations or all-cause death through Day 29 will be presented and tested using the main analysis method for Estimand 1a.	

APPENDIX J. ALGORITHM OF LOGISTIC REGRESSION METHOD

The method described in [Ge et al. \(2011\)](#) computes a population-level estimate for the treatment difference (in terms of risk difference in proportions) and supports an adjustment for the pre-defined prognostic factors.

With a data set of n participants, binary response vector $Y = (y_1, y_2, \dots, y_n)'$, covariate matrix $X = (x_1, x_2, \dots, x_n)'$, a logistic regression model assumes $\text{logit}[P(y_i = 1 | x_i)] = \beta'x_i$, where $\text{logit}(p) = \ln[p/(l - p)]$.

Let b denote the maximum likelihood estimate (MLE) of β , and its estimated variance-covariance matrix is V .

The proportions of responders to both treatment and control, and their risk difference are estimated as follows.

First, create the new covariate matrix X_t from X by adjusting the column corresponding to treatment assignment such that all participants are in the treated group. Then calculate the vector of estimated probabilities of response to treatment \hat{P}_t from X_t and b , $\hat{P}_t = \text{logit}^{-1}(X_t b)$. Similarly, assume each participant is assigned to control and redo the above steps to get X_c and \hat{P}_c .

Risk difference (RD) in proportions:

$$RD = \sum_{i=1}^n \frac{\hat{P}_{ti}}{n} - \sum_{i=1}^n \frac{\hat{P}_{ci}}{n}$$

where \hat{P}_{ti} and \hat{P}_{ci} are the i^{th} elements of \hat{P}_t and \hat{P}_c respectively.

The variance of the estimated risk difference:

$$\text{Var}(RD) = \text{Var}\left(\sum_{i=1}^n \frac{\hat{P}_{ti}}{n}\right) - 2\text{cov}\left(\sum_{i=1}^n \frac{\hat{P}_{ti}}{n}, \sum_{i=1}^n \frac{\hat{P}_{ci}}{n}\right) + \text{Var}\left(\sum_{i=1}^n \frac{\hat{P}_{ci}}{n}\right)$$

The delta method can be used to estimate each component of the variance estimation.

Define A_t as a vector with elements $A_{ti} = \hat{P}_{ti}(1 - \hat{P}_{ti})$. Similarly define A_c as a vector with elements $A_{ci} = \hat{P}_{ci}(1 - \hat{P}_{ci})$.

$$d_t = (A_t'X_t)/n$$

$$d_c = (A_c'X_c)/n$$

$$SE = \sqrt{(d_t V d_t' + d_c V d_c' - 2 d_c V d_t')}$$

The confidence interval of RD is $RD \pm Z_{(1-\alpha/2)} SE$

Log risk ratio (RR) in proportions:

$$\delta_1 = \log(RR) = \log \sum_{i=1}^n \frac{\hat{P}_{ti}}{n} - \log \sum_{i=1}^n \frac{\hat{P}_{ci}}{n}$$

where \hat{P}_{ti} and \hat{P}_{ci} are the i^{th} elements of \hat{P}_t and \hat{P}_c respectively.

The variance of the estimated log risk ratio:

$$Var(\delta_1) = Var(\log \sum_{i=1}^n \frac{\hat{P}_{ti}}{n}) - 2cov\left(\log \sum_{i=1}^n \frac{\hat{P}_{ti}}{n}, \log \sum_{i=1}^n \frac{\hat{P}_{ci}}{n}\right) + Var(\log \sum_{i=1}^n \frac{\hat{P}_{ci}}{n})$$

Consider,

$$\begin{aligned} Var\left(\log \sum_{i=1}^n \frac{\hat{P}_{ti}}{n}\right) &\approx \left(\frac{1}{\sum_{i=1}^n \frac{\hat{P}_{ti}}{n}}\right)^2 Var\left(\sum_{i=1}^n \frac{\hat{P}_{ti}}{n}\right) \approx \left(\frac{1}{\sum_{i=1}^n \frac{\hat{P}_{ti}}{n}}\right)^2 d_t V d_t' \\ Var\left(\log \sum_{i=1}^n \frac{\hat{P}_{ci}}{n}\right) &\approx \left(\frac{1}{\sum_{i=1}^n \frac{\hat{P}_{ci}}{n}}\right)^2 Var\left(\sum_{i=1}^n \frac{\hat{P}_{ci}}{n}\right) \approx \left(\frac{1}{\sum_{i=1}^n \frac{\hat{P}_{ci}}{n}}\right)^2 d_c V d_c' \\ 2cov\left(\log \sum_{i=1}^n \frac{\hat{P}_{ti}}{n}, \log \sum_{i=1}^n \frac{\hat{P}_{ci}}{n}\right) &\approx 2 \left(\frac{1}{\sum_{i=1}^n \frac{\hat{P}_{ti}}{n}}\right) \left(\frac{1}{\sum_{i=1}^n \frac{\hat{P}_{ci}}{n}}\right) d_c V d_t' \end{aligned}$$

$$SE(\delta_1) = \sqrt{Var(\delta_1)}$$

The confidence interval of $\log(RR)$ is $\delta_1 \pm Z_{(1-\alpha/2)} SE(\delta_1)$. The confidence interval of RR is $\exp(\delta_1 \pm Z_{(1-\alpha/2)} SE(\delta_1))$.

The relative risk reduction and its confidence interval is $(1 - \exp(\delta_1))$ and $[1 - \exp(\delta_1 + Z_{(1-\alpha/2)} SE(\delta_1)), 1 - \exp(\delta_1 - Z_{(1-\alpha/2)} SE(\delta_1))]$.

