4.2. Sample Size

The primary analysis is the comparison of the ADG20 arm versus the placebo arm with respect to proportion of participants infected with a non-Omicron variant of SARS-CoV-2 with a COVID-19-related hospitalization or all-cause death through Day 29.

The original required sample size was calculated based on the following assumptions obtained from a review of data from studies of other mAbs in participants with a high risk for disease progression leading to hospitalization or death prior to widespread emergence of both the Delta and Omicron variants ([AstraZeneca 2022](#); [Eli Lilly and Company 2022](#); [GlaxoSmithKline 2021](#); [Regeneron 2022](#)). The original sample size of 1084 participants was planned with 90% power, 2-sided alpha .05, and a 1:1 randomization ratio to detect a statistically significant risk reduction with a true efficacy of relative risk reduction 70% and a 5% event rate in the placebo arm.

At the time of enrollment suspension in January 2022, a total of 399 participants were randomized. Of them, approximately 320 participants will be included in the primary efficacy population of participants with a non-Omicron variant of SARS-CoV-2. Based on blinded monitoring of the primary endpoint outcomes, an aggregate event rate of approximately 9% was observed, indicating a higher placebo event rate than previously assumed and providing approximately 80% power to test the primary endpoint in the primary efficacy population given an estimated placebo event rate of 12% and the same efficacy assumption.

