The method described in [Ge et al. \(2011\)](#) computes a population-level estimate for the treatment difference (in terms of difference in proportion) and supports an adjustment for the pre-defined prognostic factors. The method relies on a logistic regression model that includes COVID-19-related hospitalization or all-cause death present or absent as the dependent variable and treatment and prognostic factors as independent variables. To define this model, consider the i th participant, $i = 1, \dots, n$, where n is the total number of participants, and let y_i denote the binary outcome for the primary endpoint (COVID-19-related hospitalization or all-cause death, present=1 or absent=0). The treatment indicator will be denoted by t_i , where $t_i = 0$ corresponds to the placebo arm and $t_i = 1$ corresponds to the treatment (ADG20) arm. The vector of prognostic factors for the i th participant will be denoted by \mathbf{x}_i . The model is given by:

$$\text{logit } p_i = \beta_0 + \beta_1 t_i + \boldsymbol{\beta}_2' \mathbf{x}_i,$$

where $p_i = P(y_i = 1)$, β_0 and β_1 are the intercept and slope, $\boldsymbol{\beta}_2$ is the vector of model parameters corresponding to the prognostic factors and the prime denotes transposition.

After the model has been fitted to the data, the model parameters will be estimated (the estimates will be denoted by $\hat{\beta}_0$, $\hat{\beta}_1$ and $\hat{\boldsymbol{\beta}}_2$, respectively). After that, two potential outcomes will be computed from the model for each participant. These outcomes represent the participant's outcomes if the participant has been assigned to the placebo and treatment arms:

$$p_{i0} = P(y_i = 1 | t_i = 0),$$

$$p_{i1} = P(y_i = 1 | t_i = 1).$$

The population-level estimates for the for the incidence rates will be defined as follows:

$$\hat{p}_0 = n^{-1} \sum_{i=1}^n p_{i0} \text{ and } \hat{p}_1 = n^{-1} \sum_{i=1}^n p_{i1}.$$

These estimates can be used to define an estimate for the treatment difference (difference in the incidence rates) or relative risk reduction in a straightforward manner, i.e.,

$$\hat{p}_1 - \hat{p}_0 \text{ and } 1 - \hat{p}_1/\hat{p}_0$$

The variance of the estimated treatment difference or relative risk reduction will be estimated using the delta method based on the algorithm presented in [Ge et al. 2011 \(Appendix J\)](#).

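### The Appendix J standard error treats covariates as fixed although the estimate is labelled population-level, so standardized intervals are slightly too narrow when ADG20 works and the covariates predict outcome

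*SAP*

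**What the plan says.** SAP 5.5.1 fits a logistic model with treatment and five covariates the SAP calls prognostic: age, sex, baseline serostatus, BMI and baseline viral load. Each participant gets a predicted risk under placebo and under ADG20. The predictions are averaged over all n participants, and the averages give the standardized risk difference and RRR. Both SAP 5.5.1 and Appendix J describe the result as population-level; in Appendix J the method "computes a population-level estimate for the treatment difference (in terms of risk difference in proportions". Appendix H gives the target population of the primary estimand as adults and adolescents with mild or moderate COVID-19 at high risk of progression.

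On variance, SAP 5.5.1 states: "The variance of the estimated treatment difference or relative risk reduction will be estimated using the delta method". Appendix J supplies the formula. The only source of uncertainty is V, the covariance matrix of the fitted coefficients, combined with gradients d_t and d_c evaluated at the observed covariates. The variance of the log relative risk uses the same pieces. No section adds a term for covariate sampling or says that inference is conditional on the observed covariates.

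**The concern.** An average of predicted risks varies for two reasons: the coefficients are estimated, and the participants averaged over are themselves a sample. Appendix J counts only the first. If the estimate is meant for the patient population in Appendix H, the second belongs in the variance. It cannot be negative, so leaving it out can only narrow the interval.

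What is at stake is the calibration of the reported 95% intervals for the standardized risk difference and RRR. This covers the primary endpoint, the two binary key secondary endpoints, and the other binary endpoints that reuse the method: medically attended visits or death, high viral load at Day 7, and viral clearance. Multiple-imputation analyses and subgroup RRRs that apply the same method inherit it.

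**Working it through.** **Inputs from SAP 4.2**
- Test and allocation: "2-sided alpha .05, and a 1:1 randomization ratio".
- Size: "approximately 320 participants will be included in the primary efficacy population", so about 160 per arm.
- Rates: "given an estimated placebo event rate of 12% and the same efficacy assumption". The efficacy assumption is a 70% reduction, so ADG20 risk is 0.12 × 0.30 = 0.036.

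**Assumed input.** The documents do not say how strongly the covariates predict outcome. I vary the SD of the prognostic linear predictor from 0.5 to 2, which corresponds to a placebo-arm c-statistic of 0.63 to 0.88.

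**Reproducing the plan's figure.** The SAP describes the trial as "providing approximately 80% power to test the primary endpoint in the primary efficacy population". With pooled variance, z = [0.084 × √160 − 1.96 × √(2 × 0.078 × 0.922)] / √(0.12 × 0.88 + 0.036 × 0.964) = (1.0625 − 0.7433) / 0.3746 = 0.852. Power is 80.3%, so the planning figures are reproduced. The original 1084 is also close: the same method gives 1076.

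**The omitted term.** Let P_t(x) and P_c(x) be the risks on ADG20 and placebo for covariates x. With a correct model and large n, the law of total variance gives

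Var(RD) ≈ (d_t − d_c) V (d_t − d_c)′ + Var_x[P_t(x) − P_c(x)] / n.

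Appendix J has the first part only. In this main-effects model the second part is zero if the treatment coefficient is zero (P_t = P_c for every patient) or if all covariate coefficients are zero. Otherwise it is positive. For log RR the matching term is Var_x[P_t(x)/mean P_t − P_c(x)/mean P_c] / n. At low risks a logistic model is close to a constant relative risk, so this term is small.

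**Size at n = 320, 12% versus 3.6%** (asymptotic, one normal prognostic score):

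| Linear-predictor SD | c-statistic | RD SE, Appendix J | RD SE with term | Ratio | Coverage without term | Log RR SE ratio | Log RR coverage without term |
|---|---|---|---|---|---|---|---|
| 0 | 0.50 | 0.02961 | 0.02961 | 1.0000 | 95.0% | 1.0000 | 95.0% |
| 0.5 | 0.63 | 0.02929 | 0.02936 | 1.0022 | 94.95% | 1.0000 | 95.0% |
| 1.0 | 0.75 | 0.02830 | 0.02853 | 1.0084 | 94.8% | 1.0007 | 95.0% |
| 1.5 | 0.83 | 0.02682 | 0.02729 | 1.0172 | 94.6% | 1.0042 | 94.9% |
| 2.0 | 0.88 | 0.02521 | 0.02592 | 1.0282 | 94.3% | 1.0119 | 94.7% |

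Coverage is 2Φ(1.96/ratio) − 1. At SD 1.0 the omitted term is 1.0084² − 1 = 1.7% of the Appendix J variance. With equal arms at 12% the ratio is 1.0000 in every row.

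For a commoner binary endpoint the log RR matters more. At an assumed 60% versus 20% with SD 1.5, its SE rises by 3.1% and coverage without the term is 94.3%.

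**Simulation with five covariates** (8,000 runs per setting, 12% versus 3.6%):

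| SD | Empirical SE | Mean SE, Appendix J | Mean SE with term | Coverage, Appendix J | Coverage with term |
|---|---|---|---|---|---|
| 0.5 | 0.03002 | 0.02912 | 0.02926 | 93.9% | 94.1% |
| 1.0 | 0.02907 | 0.02819 | 0.02851 | 94.1% | 94.4% |
| 1.5 | 0.02757 | 0.02683 | 0.02741 | 94.1% | 95.0% |

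Part of the gap to the empirical SE has another cause. At SD 1.0 the term closes 0.02851 − 0.02819 = 0.00032 of 0.02907 − 0.02819 = 0.00088, or 36%; at SD 0.5 and 1.5 the shares are 16% and 78%. The remainder is small-sample error: 160 × 0.12 + 160 × 0.036 is about 25 events for six slopes. In these settings 3% to 17% of runs were dropped for separation or extreme coefficients, so the asymptotic table is the cleaner measure.

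Under no effect (9% in both arms), rejection with the Appendix J SE was 5.1% to 5.5%, and adding the term changed it by at most 0.2 points.

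**The case against.** The best defence is that population-level may mean only marginal, that is, averaged rather than subject-specific. SAP 5.5.1 does average over the trial's own participants, and Appendix H uses the phrase as an estimand attribute. Inference conditional on the observed covariates is a recognised choice, and under it the Appendix J standard error is right. The analysis set was also shaped by variant status and by a suspension of enrollment, so random sampling of covariates is itself an assumption. This stands in part: the sponsor may choose conditional inference. But the SAP does not say it has, and a target population of patients points the other way.

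The second defence is size. Coverage falls by well under one percentage point, and the low end needs a c-statistic near 0.88. This stands, and it makes the point a small one.

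A reader might infer more than the documents support:
- **That the primary test is compromised.** It is not, because the term vanishes when there is no effect.
- **That every interval is affected whenever the drug works.** The covariates must also predict outcome. The Miettinen-Nurminen interval for the observed difference does not use this formula.
- **That all key secondary and virologic endpoints are affected.** Time to sustained resolution and duration of viral shedding use Kaplan-Meier and Cox methods. Change in viral load and viral load AUC use ANCOVA or MMRM. None relies on Appendix J.
- **That the omission explains all under-coverage seen in simulation.** Small-sample error contributes as well.

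**Conclusion.** The concern holds as a small mismatch between formula and label. For a population-level estimand, the Appendix J intervals are slightly too narrow if ADG20 has an effect and the covariates are prognostic. At the planning figures the unconditional standard error is 0.2% to 2.8% larger for the risk difference and 0.0% to 1.2% larger for the log relative risk. Nominal 95% coverage without the term is about 94.95% to 94.3% and 95.0% to 94.7% respectively.

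This rests on the assumed linear-predictor SD of 0.5 to 2, a correctly specified main-effects logistic model, and large-sample theory. No confirmatory decision should change. The correction is worth making because it is cheap and the error runs in one direction.

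**What to change.** In Appendix J:
- add (1/n) × the sample variance of (p_ti − p_ci) to Var(RD);
- add (1/n) × the sample variance of (p_ti/mean p_t − p_ci/mean p_c) to Var(log RR).

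An equivalent robust unconditional variance or a bootstrap would also serve. Use the same variance for every binary endpoint that reuses the method. If inference conditional on the enrolled covariates is intended, say so in Appendix J and SAP 5.5.1 and drop the population-level description; the formula can then stay.

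The cost is two lines of text and code and no new data. Risk-difference intervals widen by roughly 0.2% to 3%, usually about 1%. The change does not cure small-sample error from few events. It belongs before the SAP is signed, which SAP 3.2 places before unblinding. At the same time, Appendix I should point to Appendix J for the delta method; it now points to Appendix K, which holds the criteria for potentially clinically significant values.
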